3.10. Materials needed to conduct the clinical investigation

- *Collagen Medical Device (MD-Tissue)* 2-mL vials in sufficient numbers for the needs of the clinical investigation.

This material will be sent by Guna S.p.a. to the pharmacy of each Experimental Center in suitable quantity for conducting the study.

3.11. Gruppi in studio

- **Group A (Collagen Medical Device):**

This Experimental Group will be treated with subcutaneous (s.c.) injections of 2 ml volume of:

- MD-Tissue (GUNA, Milan-Italy)

[figure not shown]
Composition for 2 ml: collagen 100 micrograms

Excipients: Ascorbic acid, Magnesium gluconate, Pyridoxine hydrochloride, Riboflavin, Thiamine hydrochloride, NaCl, Water for injection.

Subjects will be treated with No. 6 peri-tendon injections (2 infiltrations per week for three weeks).

- **Group B:**

This Experimental Group will implement only physiotherapy (eccentric strengthening protocol) for a period of 6 weeks.

3.12. Eccentric strengthening protocol

Both Group A and Group B will undergo a 6-week eccentric training protocol of the plantar ankle flexor muscles of the affected side. The exercises will be shown to each patient by the investigating physician at the time of enrollment; a physiotherapy booklet will also be provided to each patient, which will provide all the information to repeat the exercises at home. The exercise program will be as follows:

[figure not shown]
1. Ankle plantar flexor muscles stretching in orthostatic position (gastrocnemius stretching: figure 1a; soleus stretching: figure 1b) - 3 repetitions of 30".
2. Eccentric reinforcement 1: on a step, starting from a plantar flexion position the patient with slightly flexed knee (Figure 2a) reaches maximum ankle dorsiflexion in 5" - return to starting position using the contralateral limb for pushing (Figure 2b) - 3 sets of 15 repetitions each.
3. Eccentric reinforcement 2: On a step, starting from a plantar flexion position the patient with extended knee (Figure 3a) reaches maximum ankle dorsiflexion in 5" - return to starting position using the contralateral limb for pushing (Figure 3b) - 3 sets of 15 repetitions each.
4. Finish with ice application on Achilles tendon (1' application followed by 1' break) - repeat 3 times.

The entire protocol will be repeated 2 times a day, every day.

Patients will be asked to gradually increase the intensity of the exercises, including applying an overload of up to 5 kg, based on their ability to endure the exercise without pain and discomfort at the Achilles tendon region.

In Group A, the exercises will begin on the day of the first infiltration session.

To increase adherence to the intervention protocol, a physiotherapy booklet will be distributed with tables containing dates indicating the days the patient performed the protocol exercises, also with blanks to add any notes on medication use or complications that occurred.

3.13. Diagnosis of achilles tendinopathy

Subjects with symptomatology referable to Achilles tendinopathy will be included in the clinical investigation: tenderness on palpation, relief on palpation of increased size of the Achilles tendon compared with the contralateral. The clinical diagnosis will have to be confirmed ultrasonographically.

3.14. Criteria of effectiveness

3.14.1 Primary Endpoint

The primary end point will be assessed at T8s/FU and will involve:

- Assessment of the VISA-A questionnaire score at time T8w/FU compared to time T0. A difference between the two groups of 12 out of 100 points on the questionnaire can be considered clinically significant [17].

3.14.1. Secondaries End Points

- Evaluation of VISA-A score at time T3w and T6w/FU compared to time T0
- Assessment of the VAS score at time T3w, T6w/FU and T8w/FU compared to time T0
- Evaluation of the SF12 questionnaire at time T3w, T6w/FU, and T8w/FU compared to time T0.
- Evaluation of the fraction of subjects in each group achieving Minimal Clinical Disease (MCD) considering that the MCD of the VISA-A questionnaire is 18.5 (90% MCD).
- Assessment of analgesic drug unit consumption based on clinical diary at time T3w, T6w/FU and time T8w/FU (paracetamol 1000 mg. will be used as "rescue dose" in case of onset/recurrence of pain).
- Evaluation of the fraction of subjects in each group who drop out early in relation to Adverse Events (AE/SAE/SUSAR).

3.15. Early abandonment of the clinical study

Subjects may leave the clinical study for the following reasons:

- a. at their own request (even without a reason);
- b. at the discretion of the investigator.
- c. if they incur an Adverse Event.

Subjects who drop out of the clinical study before its completion will undergo a final evaluation similar to the subjects who completed it, unless the subject expressly declines.

The reason for abandonment will be reported on the Data Collection Form.

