3.9. Procedures

3.9.1 Timing of assessment

T0 baseline: VISIT enrollment; prior to start of treatment.

T1 week: first and second treatment sessions + physiotherapy

T2 weeks: third and fourth treatment sessions + physiotherapy

T3 weeks: VISIT fifth and sixth treatment session + physiotherapy

T6 weeks/FU: VISIT - end of physiotherapy

T8 weeks/FU: VISIT - end of clinical investigation.

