4. STATISTICS

4.14. Sample size

A one-covariance analysis for two arms of 28 subjects each, in which the covariate of interest differs by 12 units in its mean value between the two arms (compared with a null hypothesis of no difference), with a common standard deviation assumed to be 15 units, and an R^2 value assumed to be 0.2 has a

power of 90.75% in discriminating the established difference between mean values, using an F-test at a significance level of 0.05.

Assuming dropout patients to be 20% of the total, the inflated sample size of the protocol becomes 36 patients per arm.

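### Section 3.15 treats early stopping only as leaving the study, does not date the leaver's final evaluation, and provides for no week-8 VISA-A after treatment is stopped

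*Protocol*

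**What the plan says.** The primary endpoint (Protocol, section 3.14.1) is "Assessment of the VISA-A questionnaire score at time T8w/FU compared to time T0".

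Section 3.15 lists three reasons for leaving the study: the subject's request, the investigator's discretion, and "if they incur an Adverse Event". It then states: "Subjects who drop out of the clinical study before its completion will undergo a final evaluation similar to the subjects who completed it", with the exception "unless the subject expressly declines". The reason for leaving is recorded. The combined protocol and SAP has the same rule.

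Section 3.9.1 sets the calendar:

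- "T3 weeks: VISIT fifth and sixth treatment session + physiotherapy"
- "T6 weeks/FU: VISIT - end of physiotherapy"
- "T8 weeks/FU: VISIT - end of clinical investigation"

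VISA-A, VAS and SF-12 are scheduled at T0, T3, T6 and T8 only. Tab. 1 has no column for an early-exit visit. Section 4.15 names ANCOVA for the primary endpoint but gives no analysis set, no missing-data rule and no rule for scores taken off schedule.

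**The concern.** Three things are left open. The evaluation of a leaver has no date. The only status described for a subject who stops early is leaving the study; nothing describes stopping injections or exercise while still answering the questionnaires. And no sentence asks such a subject for a T8w VISA-A, the one score that the primary analysis needs.

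This matters more here than in a trial with matched arms. Group A receives six injections and Group B receives physiotherapy only, with no sham (sections 3.3 and 3.11). A reaction to an injection can therefore lead to an exit only in Group A. Missing week-8 scores can then differ between arms in number and in kind, and the randomised comparison loses some of its protection. A subject who leaves before T3 has no scheduled post-baseline VISA-A at all, so a later model would have little to work from.

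**Working it through.** **1. The plan's own figures.** Section 4.14 assumes a difference of 12 points ("differs by 12 units in its mean value between the two arms"), SD 15, R² 0.2, 28 per arm and an F-test at 0.05.

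- Residual SD = 15 × √(1 − 0.2) = 13.416.
- Standard error at 28 per arm = 13.416 × √(2/28) = 3.586.
- Noncentrality = 12 / 3.586 = 3.347, with 2 × 28 − 3 = 53 df. Power = 0.9075, which matches the stated 90.75%.
- Dropout inflation: 28 / 0.8 = 35 per arm. The plan uses 36, which is close enough. The sample size is not in error on this point.

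**2. How many subjects are affected.** 0.20 × 72 = 14.4. Enrolled minus evaluable = 72 − 56 = 16. So about 14 to 16.

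**3. Shortfall of an early score.** The documents give no expected gain and no exit times. Assumptions: the gain from T0 to T8 is 15 to 20 points, it is linear over 8 weeks, and exits are evaluated at week 2. (The 18.5-point responder threshold in the secondary endpoints lies inside that range.) A week-2 score then carries 2/8 of the gain and misses 6/8:

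- 0.75 × 15 = 11.25 points; 0.75 × 20 = 15 points.

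**4. If exit scores were used as T8: unequal exits.** Assume a 10-percentage-point difference in exits and take the gain common to both arms:

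- 0.10 × 11.25 = 1.1 points; 0.10 × 15 = 1.5 points, against the arm with more exits.
- Relative to the planned 12 points: 1.125/12 = 9% to 1.5/12 = 13%.
- Relative to the standard error at 36 per arm, 13.416 × √(2/36) = 3.16: about 0.36 to 0.47 of one standard error.

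**5. If exit scores were used as T8: equal exits.** Let both arms lose 20% and let the exit score carry a fraction f of the week-8 treatment effect. The expected difference is 12 × [1 − 0.20 × (1 − f)]. Power is for 36 per arm with the residual SD unchanged.

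| f | Expected difference | Power |
|---|---|---|
| 0 | 9.6 | 84.9% |
| 0.25 (week 2, linear) | 10.2 | 88.9% |
| 0.5 | 10.8 | 92.0% |
| 1 | 12.0 | 96.3% |

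In the week-2 case the loss is 0.20 × 0.75 × 12 = 1.8 points.

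**6. If exit scores are excluded.** With 28 per arm the planned 90.75% power remains, but up to 16 of 72 randomised subjects (22%) have no primary outcome, possibly for reasons that differ by arm.

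**The case against.** A reader might infer that leavers are evaluated at exit instead of at week 8. The text does not say so. It gives no timing, and since the completers' final evaluation is the T8w visit, a similar evaluation could mean a visit at week 8. Exit is the more natural reading, because the subject is leaving and may decline, but it is not the only one. The gap remains under either reading, since sites could apply the rule differently.

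A reader might also infer that follow-up ends when treatment ends. That is not supported. Section 3.15 is permissive and concerns leaving the study. Nothing in it says that stopping injections or exercise forces withdrawal, and by design follow-up continues after the injections (week 3) and the exercise (week 6). What stands is narrower: continued follow-up after early stopping is not provided for.

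The harm in steps 4 and 5 needs exit scores to be entered as T8 scores, and section 4.15 contains no such rule. The point sizes are therefore conditional. The gain, its linearity, the week-2 exits and the imbalance are all assumptions.

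The sample size already absorbs 20% loss, and the T3 and T6 scores could support a repeated-measures analysis for later leavers. Both points stand. However, inflating the sample size protects power and does not protect against arm-related missingness, and interim scores help only under assumptions that the data cannot test. Finally, some leavers will decline any contact, so the number of scores gained is unknown.

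**Conclusion.** The point holds as a gap in what the trial collects. It does not show that the wrong time point was chosen, and it does not show an error in the sample size. Section 3.15 does not date the leaver's evaluation and does not secure a T8w VISA-A after treatment stops. With injections in one arm only, the resulting missing data can depend on arm.

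The size is modest. About 14 to 16 of 72 subjects are exposed at the planned dropout rate. If exit scores were used, the shift is about 1.1 to 1.5 points for a 10-percentage-point imbalance, or a loss of about 1.8 of the planned 12 points with equal 20% exits, under the assumptions in steps 3 to 5. Equal exits are therefore not harmless when the arms truly differ. If exit scores are not used, the cost is up to 16 missing primary outcomes. This is worth correcting because the correction is cheap and an uncollected week-8 score can afterwards only be modelled.

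**What to change.** In section 3.15, of both documents:

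- Define stopping study treatment and withdrawing from follow-up as two separate events, each recorded with date and reason.
- Ask every subject who stops injections or exercise but does not refuse contact to complete VISA-A, VAS and SF-12 at the scheduled T3, T6 and T8 dates, by post or telephone if they will not attend.
- Keep the exit evaluation for subjects who decline further contact. Record it under its actual date and never use it as T8.

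In section 4.15, state that T8w scores collected after treatment was stopped enter the primary ANCOVA by randomised group, and state how subjects who still have no T8w score are handled.

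No treatment or stopping rule changes. The cost is a paragraph in section 3.15, a sentence or two in section 4.15, one line in the consent form, and a few extra questionnaire contacts for at most about 16 subjects. Some leavers will still decline, so the gap will shrink but may not close.

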4. STATISTICS

4.14. Sample size

A one-covariance analysis for two arms of 28 subjects each, in which the covariate of interest differs by 12 units in its mean value between the two arms (compared with a null hypothesis of no difference), with a common standard deviation assumed to be 15 units, and an R^2 value assumed to be 0.2 has a

power of 90.75% in discriminating the established difference between mean values, using an F-test at a significance level of 0.05.

Assuming dropout patients to be 20% of the total, the inflated sample size of the protocol becomes 36 patients per arm.

4.15. Plan of statistical analysis

The primary endpoint will be evaluated by Ancova, as described in the numerosity calculation.

Secondary endpoints will be assessed as follows: 1) the VISA-A score at time T3s and T6s/FU compared with time T0 with Anova at repeated measures between group and within group; 2) the VAS at time T3s, T6s/FU and T8s/FU compared with time T0 with Anova at repeated measures between group and within group; 3) the SF12 questionnaire at time T3s, T6s/FU and T8s/FU compared with time T0 with Anova at repeated measures or Friedman's test; 4) the fraction of subjects in each group reaching Minimal Clinical Disease (MCD) considering that the MCD of the VISA-A questionnaire is 18.5 (90% MCD) with Fisher's exact test; 5) the units of analgesic drug consumed according to the clinical diary at time T3s, T6s/FUs and time T8s/FUs (paracetamol 1000 mg will be used as "rescue dose" in case of pain onset/recrudescence) with Friedman's exact test; 6) the fraction of subjects in each group who drop out of the investigation early in relation to Adverse Events (AE/SAE/SUSAR) with Fisher's exact test.

Statistical significance will be assumed for $p < 0.05$, unless corrected for multiple testing.

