3.5. Participant population

A total of 72 subjects with achilles tendinopathy will be enrolled. The recruitment phase will be closed no sooner than the number of subjects in the clinical investigation plan has been reached.

Only subjects will be included in the two experimental groups:

- belonging to the departments of the experimental centers;
- who meet the inclusion criteria and have no exclusion criteria.

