3.8. Randomization and codification of subjects

Recruited subjects will be placed in Group A or B according to a 1:1 randomization list with 10 blocks of 9 subjects generated by software (2 blocks for each experimental center); the use of blocks will result in balanced groups.

A randomization list is planned for each Experimental Center comprising 18 subjects; the inclusion of subjects within the two experimental groups will take place progressively following the order of enrollment. Competitive enrollment is established among the participating Experimental Centers, which will end when the 72 subjects under the Clinical Investigation Plan have been enrolled. Each Experimental Center will be allowed to enroll a maximum of 18 subjects.

The randomization list will be kept by each Principal Investigator and the Clinical Research Unit of Guna S.p.a.

At the time of enrollment, each subject will be assigned a complex alphanumeric identification code consisting of the progressive enrollment number followed by an alphanumeric code generated through *Random Sequence Generator* at www.random.org.

The complex code is found to be in compliance with the current Privacy Regulations regarding coding of subjects participating in clinical trials.

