### 3.8. Randomization and codification of subjects

Recruited subjects will be placed in Group A or B according to a 1:1 randomization list with 10 blocks of 9 subjects generated by software (2 blocks for each experimental center); the use of blocks will result in balanced groups.

A randomization list is planned for each Experimental Center comprising 18 subjects; the inclusion of subjects within the two experimental groups will take place progressively following the order of enrollment. Competitive enrollment is established among the participating Experimental Centers, which will end when the 72 subjects under the Clinical Investigation Plan have been enrolled. Each Experimental Center will be allowed to enroll a maximum of 18 subjects.

The randomization list will be kept by each Principal Investigator and the Clinical Research Unit of Guna S.p.a.

At the time of enrollment, each subject will be assigned a complex alphanumeric identification code consisting of the progressive enrollment number followed by an alphanumeric code generated through *Random Sequence Generator* at [www.random.org](http://www.random.org).

The complex code is found to be in compliance with the current Privacy Regulations regarding coding of subjects participating in clinical trials.

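### Randomisation is stratified by centre, but the primary ANCOVA has no centre term

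*Protocol*

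**What the plan says.** **Randomisation (section 3.8, both documents).** Allocation follows a "1:1 randomization list with 10 blocks of 9 subjects generated by software (2 blocks for each experimental center"). The lists are separate by centre: "A randomization list is planned for each Experimental Center comprising 18 subjects". Enrolment is competitive up to the total of 72, with a cap: "Each Experimental Center will be allowed to enroll a maximum of 18 subjects".

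**Primary endpoint (section 3.14.1).** "Assessment of the VISA-A questionnaire score at time T8w/FU compared to time T0".

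**Primary analysis (section 4.15).** "The primary endpoint will be evaluated by Ancova, as described in the numerosity calculation". The calculation referred to, in section 4.14, opens with "A one-covariance analysis for two arms of 28 subjects each". It assumes a difference of 12, an SD of 15, an R² of 0.2 and an F-test at 0.05, and states a power of 90.75%.

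The covariate is not named. Centre does not appear in sections 4.14 or 4.15 as a factor, covariate, random effect or sensitivity analysis. The Combined protocol and SAP repeats these sections with the same content, so it does not supply a fuller model.

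**The concern.** Separate blocked lists keep the arms roughly balanced within each centre. That removes most of the between-centre variation from the true error of the treatment comparison. A model without centre leaves the same variation in its residual. The estimate remains unbiased, but the reported standard error is then larger than the true one, the confidence interval is wider than it need be, and the test is mildly conservative. The usual principle is that factors used to restrict the randomisation enter the primary model, and that this is settled before any data are seen.

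What is at stake is precision and a match between design and analysis. No primary conclusion is at risk.

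**Working it through.** **Inputs.** From section 4.14: 28 per arm, difference 12, SD 15, R² 0.2, alpha 0.05. From sections 3.5 and 3.8: 72 subjects, at most 18 per centre, 10 blocks at 2 per centre. The number of centres is inferred: 10/2 = 5 from the blocks, and at least 72/18 = 4 from the cap.

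**1. Reproduce the stated power.** Residual variance after the covariate is 225 × (1 − 0.2) = 180, so the residual SD is 13.42. The noncentrality is (28/2) × 12²/180 = 11.2. Residual df with arm and one covariate are 56 − 2 − 1 = 53. The noncentral F gives 90.749%, which is the stated 90.75%.

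**2. Which model does that figure match?** With the same noncentrality:

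| Residual df | Model | Power |
|---|---|---|
| 54 | arm only | 90.77% |
| 53 | arm + 1 covariate | 90.75% |
| 52 | arm + 2 covariates | 90.73% |
| 50 | arm + covariate + 4 centres | 90.69% |
| 49 | arm + covariate + 5 centres | 90.66% |

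Only 53 df matches to two decimals. This agrees with the wording of section 4.14.

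**3. Effect of leaving centre out.** The documents give no between-centre variance, so the centre share of the residual variance of 180 was set at 0, 5, 10 and 20%. Blocks of 9 cannot be split 1:1, so two list schemes were assumed: each block split 5:4 or 4:5 at random, or each list of 18 split 9:9. Four enrolment patterns were assumed: four equal centres, five equal centres, rates 3:2:2:1:1, and rates 1:1:1:1:0.1. That makes 8 scenarios of 40,000 trials each, with competitive enrolment to 72, the cap of 18, 56 random completers, and a true effect of 0 or 12. Both models were fitted to the same data. Ranges are over the 8 scenarios; half-widths are of the 95% confidence interval in VISA-A points.

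| Centre share | Power without centre | Power with centre | Change (points) | Type I error without centre | Half-width without | Half-width with |
|---|---|---|---|---|---|---|
| 0% | 89.7-90.2% | 88.6-89.7% | −0.5 to −1.1 | 4.7-5.1% | 7.24-7.25 | 7.30-7.38 |
| 5% | 90.2-90.7% | 90.2-91.0% | −0.1 to +0.4 | 4.5-4.9% | 7.20-7.22 | 7.12-7.20 |
| 10% | 90.8-91.3% | 91.6-92.4% | +0.8 to +1.1 | 4.2-4.7% | 7.16-7.18 | 6.93-7.00 |
| 20% | 91.9-92.5% | 94.4-94.9% | +2.3 to +2.6 | 3.7-4.2% | 7.06-7.11 | 6.53-6.60 |

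Monte Carlo standard errors are 0.07-0.10 points for the power difference and about 0.11 points for type I error. The mean error of the estimate without centre was at most 0.05 VISA-A points, so there is no bias.

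A separate simulation with exact balance (four centres of 14, 20,000 runs) gave type I error of 4.8, 4.6, 4.1 and 3.4% without centre at the same four shares, against 4.8-5.1% with it.

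**4. Break-even.** Interpolating linearly between the simulated shares, adding centre neither gains nor loses power at a share of 2.9-3.4% with four centres and about 4.5-5.6% with five.

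**5. Small centres.** No fit failed in 8 × 40,000 = 320,000 trials. In the 1:1:1:1:0.1 pattern the smallest centre had fewer than 4 completers in 93% of trials, and some centre had completers in one arm only in 48-49%.

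**The case against.** The strongest reply is that the plan as written does no harm: no bias, no inflated error, power near 90%. That stands, and it is why the point is minor.

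The power gain is also not assured. Its sign depends on a centre variance the documents do not give, and the common written exercise programme (section 3.12) and the VISA-A entry window of 50 to 75 (section 3.6) may keep that variance low. This stands too, so the recommendation does not rest on power.

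The match at 53 df separates models by only hundredths of a point, and shows what went into a sample-size calculation rather than what will be fitted. That is fair: the df match is supporting evidence, and the main evidence is that section 4.15 points to a one-covariate model.

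It can be said that silence does not exclude centre. But if the choice were left until the data are seen and the more favourable model reported, simulated type I error would be 5.5-6.1%. This does not follow from the plan if its one-covariate model is kept to, so it is only a reason not to leave the matter open.

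Finally, under fixed centre effects a centre with completers in one arm only adds nothing directly to the arm comparison. That is a real cost of the fix with very small centres, and it is included in the simulated losses.

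**Conclusion.** The concern holds and is minor. Randomisation is stratified by centre, and the primary model to which section 4.15 refers has no centre term. Leaving it out makes the test conservative if centres differ: type I error is 4.2-4.7% at an assumed centre share of 10%, and 3.7-4.2% at 20%. Adding centre changes power by between −1.1 and +2.6 points over shares of 0 to 20%. These sizes depend on the assumed shares, number of centres, enrolment patterns and list schemes. The mismatch between design and model does not depend on them.

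**What to change.** State the primary model in section 4.15 in one sentence: VISA-A at T8w on arm, T0 VISA-A and centre as a fixed factor, reporting the adjusted difference between Groups A and B with its 95% confidence interval. T0 VISA-A is inferred from the endpoint definition in section 3.14.1, so the sponsor should confirm it as the covariate. With T0 in the model, analysing the T8w score or the change from T0 gives the same arm difference and standard error. The sentence can be part of any wider rewrite of the primary model. No rule for pooling small centres is needed to fit it.

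The cost is one line of text and 3 or 4 residual df (53 to 50 with four centres, 49 with five). With arms balanced within centres this takes power from 90.75% to 90.69% or 90.66%. In the simulations it cost 0.5-1.1 points if centres do not differ at all. The sample size need not change, and each subject's centre is already known.

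### The T8-only ANCOVA has no missing-data method and leaves the T3 and T6 VISA-A scores unused; if dropout depends on scores differently by arm, the primary effect could be biased by roughly 1 to 3 points either way

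*Protocol*

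**What the plan says.** Section 3.14.1 (Primary Endpoint) of the Protocol defines the endpoint as "Assessment of the VISA-A questionnaire score at time T8w/FU compared to time T0". Section 4.15 gives the whole primary analysis: "The primary endpoint will be evaluated by Ancova, as described in the numerosity calculation". The calculation it points to, in section 4.14, is "A one-covariance analysis for two arms of 28 subjects each". The target "differs by 12 units in its mean value between the two arms", "with a common standard deviation assumed to be 15 units", R² is 0.2, and power is 90.75% for an F-test at 0.05. Section 4.14 then adds: "Assuming dropout patients to be 20% of the total, the inflated sample size of the protocol becomes 36 patients per arm".

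Table 1 in section 3.9.2 schedules VISA-A at T0, T3, T6 and T8. Section 4.15 uses the T3 and T6 scores only for a secondary endpoint, by repeated-measures ANOVA. Section 3.15 says that subjects who leave early "will undergo a final evaluation similar to the subjects who completed it", unless they decline. It does not say when this takes place or whether the score counts as T8.

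The Combined protocol and SAP has the same text on all these points. Neither document defines an analysis set, a missing-data method or a sensitivity analysis for the primary endpoint.

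**The concern.** The plan expects about one subject in five to leave but does not say how they enter the primary analysis. Inflating 28 to 36 per arm makes sense mainly if leavers contribute nothing at T8, so the natural reading is an ANCOVA of those with a T8 score. That analysis estimates the randomised comparison without bias only if leaving is unrelated to outcome given T0 VISA-A, or related in the same way in both arms.

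The design gives reason to doubt this. Group B has physiotherapy alone with no sham injection, so subjects know their arm, and section 3.15 lets them leave at their own request or at the investigator's discretion. Scores that could correct much of the resulting bias are already collected but not used. The silence also lets a completer, last-value or model-based analysis be chosen after the data are seen. If a withdrawal evaluation made before week 8 were placed in the T8 slot, an early score would be read as an 8-week score.

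**Working it through.** **Inputs from the documents (sections 4.14 and 3.14.1).** Difference 12, SD 15, R² 0.2, 28 per arm, two-sided alpha 0.05, dropout 20%, 36 per arm enrolled. I assume that the single covariate is T0 VISA-A.

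**Step 1: reproduce the stated power.** Residual variance = 15² × (1 − 0.2) = 180. Variance of the adjusted difference = 180 × (1/28 + 1/28) = 12.857, so SE = 3.586. Noncentrality = 12²/12.857 = 11.2. With F on 1 and 53 df, power = 90.75%, an exact match.

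**Step 2: effect of losing 20%.** 28/0.8 = 35, and the plan enrols 36; 36 × 0.8 = 28.8 remain per arm. Power is 90.75% at 28/28, 91.2% at 29/28 and 91.7% at 29/29. Uneven loss alone costs little: 33/24 gives 90.6% and 34/23 gives 90.2%.

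**Step 3: simple bias arithmetic (assumed inputs).** Let q be an arm's dropout rate and g the amount by which completers' T8 scores exceed those that dropouts would have had. The completer mean exceeds the full-arm mean by q × g, so the bias in A minus B is (q_A − q_B) × g. The documents give neither quantity. I take g = 5 to 15 points.

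- 20% and 20%: 0
- 15% and 25% (A, B): −0.5 to −1.5
- 10% and 30%: −1 to −3
- 25% and 15%, or 30% and 10%: the same sizes with a plus sign

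**Step 4: simulation (assumed inputs, 4,000 runs per scenario).** 36 per arm; SD 15; correlation of T0 with later visits 0.447 (√0.2); T3–T6 0.75, T3–T8 0.6, T6–T8 0.8; true T8 effect 12. Subjects leave after T6. Where leaving is score-related, the log odds change by 0.7 per SD of the T6 score. The last column is a regression estimate that uses T0, T3 and T6 for all randomised subjects.

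| Dropout scenario | Completer ANCOVA | Rejection rate | Using T3 and T6 |
|---|---|---|---|
| Random, 20% in each arm | 12.0 | 91% | 12.1 |
| Same score-related mechanism, 20% in each arm | 12.0 | 91% | 11.9 |
| Poor scorers leave, 10% A and 30% B | 10.9 | 85% | 12.0 |
| Poor scorers leave, 30% A and 10% B | 13.0 | 95% | 11.9 |
| About 20% in each arm, score-related in B only | 10.7 | 85% | 12.0 |
| About 20% in each arm, opposite mechanisms | 9.6 | 76% | 12.0 |

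With stronger score-related leaving in one arm only, the bias reaches about 2.7 points and power falls to about 74%. Under random dropout the estimate using T3 and T6 has an empirical SE of 3.40 against 3.61, about 6% smaller (3.40/3.61 = 0.94); across settings the gain is about 2% to 7%.

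**Step 5: cross-check by formula at 28/28.** An effect shrunk to 11 gives noncentrality 11²/12.857 = 9.41 and power 85.4%; an effect of 10 gives 7.78 and 78.2%. With no true effect, a bias of 1.2 gives 1.2/3.586 = 0.335 and a two-sided rejection rate of 6.2%; a bias of 2.7 gives 0.753 and 11.5%. A full 3-point bias would go slightly beyond these ranges: power 69.3% at an effect of 9 (noncentrality 9²/12.857 = 6.3), and rejection 13.0% under no effect.

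**The case against.** The strongest objection is that ANCOVA at the final visit is a standard analysis and was correctly sized. A reader might infer that the expected 20% dropout takes power below 90.75%. It does not: that figure is already net of the loss (Step 2).

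A reader might also infer that poor scorers will leave Group B and so mask a benefit. The documents give no dropout by arm and no link between leaving and score. Group A alone has six injections, and adverse events are a listed reason to leave, so excess loss in Group A is as plausible. That pattern would overstate the benefit.

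The false-positive figure is also easy to misread as false claims for the device. With a bias of 2 points against Group A and no true effect, the rejection rate of 8.5% splits into about 7.9% favouring physiotherapy alone and 0.6% favouring the device. The split reverses if the bias is reversed.

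Nor does the plan say that leavers are excluded. That is an inference, and section 3.15 does plan a final evaluation for them.

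On method, multiple imputation using T3 and T6 would keep the planned ANCOVA, so a mixed model is not the only remedy. The near-perfect recovery in Step 4 is expected because simulated leaving depended on an observed score. Subjects who leave before T3 have no scheduled post-baseline VISA-A for any model to use.

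All of this stands as a limit on direction and size. It does not supply the missing method or explain why the T3 and T6 scores stay out of the primary analysis.

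**Conclusion.** The point holds in conditional form. The primary analysis is a T8-only ANCOVA with no missing-data method, and its natural reading leaves the collected T3 and T6 scores unused. Expected dropout by itself leaves power at 90.75% to 91.7%. If leaving is related to earlier scores differently in the two arms, the completer estimate is biased by roughly 1 to 3 points in either direction, which is 8% to 25% of the 12-point target (1/12 to 3/12). If the mechanism is the same in both arms, the bias is about zero.

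In the simulated scenarios, bias towards zero lowers power to about 74% to 85%. Bias away from zero overstates the benefit. With no true effect, the two-sided false-positive rate is about 6% to 12%. All these sizes rest on assumed dropout rates, dropout–score relations and visit correlations. The change should be made before the data are seen, but the sample size need not change.

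**What to change.** In section 4.15, make the primary analysis a likelihood-based repeated-measures model in all randomised subjects. The outcome is VISA-A at T3, T6 and T8; the terms are T0 VISA-A, arm, visit, arm-by-visit and centre, with unstructured covariance. The T8 contrast between arms is the primary result. Multiple imputation using T3 and T6, followed by the planned ANCOVA, is an acceptable equivalent.

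State that the section 3.15 evaluation is assigned to a visit by its actual date, so that it counts as T8 only if made within a defined week-8 window. Keep the completer ANCOVA as a supportive analysis. Add a sensitivity analysis for data not missing at random, for example a delta adjustment applied by arm.

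The cost is plan wording and slightly more analysis work, with no new visits or subjects. The model relies on a missing-at-random assumption, and it helps little for subjects who leave before T3 without a post-baseline score.
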